Date: 06/25/2019

Version Number: 1

Principal Investigator: [name], OTD, PhD, OTR/L

Application Number: 2015868

Application Title: Efficacy of Metacognitive-Strategy Training to Improve Activity Performance and Reduce Motor Impairment in Sub-Acute Stroke

Protocol

1. Abstract

The long-term goal of this research is to improve activity performance and reduce motor impairment in individuals with stroke. There are two primary gaps in current stroke rehabilitation practice that must be addressed to achieve this goal: (1) current impairment-based approaches (e.g. motor) are not improving meaningful activity performance; and (2) current stroke rehabilitation interventions are often not designed to be clinically feasible and are rarely implemented into practice. The overall hypothesis of this proposal is that a clinically-feasible, activity-based intervention, metacognitive strategy training (MCST), will produce a significant improvement on objective and subjective measures of activity performance and motor function in comparison to a usual care occupational therapy (OT) group. These gains will transfer and generalize to untrained tasks in novel environments. The specific aims of this project are: (1) to evaluate the efficacy of MCST to improve subjective and objective activity performance in individuals with subacute stroke; and (2) to evaluate the efficacy of MCST to improve motor function in individuals with subacute stroke. Participants with subacute stroke living in the community with self-identified activity performance goals and hemiparesis will be recruited through a local stroke registry ($n = 108$). Those individuals who meet inclusion and exclusion criteria will be randomized to either a MCST group or to a usual care occupational therapy group. Both groups will receive ten, 45 minute sessions of treatment. Treatment outcomes will be assessed baseline, post-intervention, and at three-months post-intervention. Treatment efficacy outcomes will be analyzed with an intent-to-treat model with an analysis of covariance (ANCOVA). Potential covariates will include age, stroke severity, degree of cognitive impairment, and degree of motor impairment. Independent samples t-test and chi-square test will be used to ensure successful randomization and balance between groups. Group differences at baseline that are statistically significant will also be considered as covariates in the analysis. Post-hoc tests will be employed as appropriate. Significance levels, effect sizes, and confidence intervals will be reported. Completion of this study is likely to result in an efficacious, clinically feasible intervention to improve activity performance and reduce motor deficits in individuals with stroke that can be feasibly implemented into current systems of care. The proposed study and anticipated outcomes are consistent with the research priority of the National Center for Medical Rehabilitation Research (NCMRR), which is to focus on identifying, preventing, and treating key secondary conditions that are associated with physical impairments and disabilities, including stroke.

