Canadian Occupational Performance Measure (COPM)	T1, T2, T3	The COPM is a semi-structured interview guide for establishing a subject's activity performance levels within self-care, leisure, and productivity. The subject will set a minimum of 5 activity goals, providing a self-rating of 1-10
Performance Quality Rating Scale (PQRS)	T1, T2, T3	The PQRS is an observational, objective method of scoring subject activity performance of goals set via the COPM. A blind, trained rater external to the research study team will view video recordings of each subject performing goals. Each goal is rated on a scale of 1 (no activity criteria were met) to 10 (all activity criteria were met). The final score will be an average of all 5 goals.
National Institutes of Health (NIH) Toolbox Cognition Battery	T1, T2, T3	The NIHTB-CB is a collection of 7 computer-based measures assessing episodic memory, executive function and attention, working memory, language, and processing speed. As a whole, the NIH-CB is a brief assessment of fluid intelligence including problem-solving, judgment, thinking, and memory. In the present study, the fluid cognition composite T-score representing executive function will be used as an outcome measure.
Upper Extremity Fugl-Meyer	T1, T2, T3	The Fugl-Meyer is a well-established measure of upper extremity motor performance in individuals with post-stroke hemiparesis. Each item is scored either a 0 (cannot perform), 1 (performs partially), or 2 (performs fully) with a maximum score of 66.

		In the present study, the upper extremity scaled scored will be utilized.
Patient Health Questionnaire (PHQ-9)	T1, T2, T3	The PHQ-9 is a self-report measure of depressive symptoms. The subject identifies how often over the previous 2 weeks they have experienced 9 depressive symptoms. The total score reflects the severity of depressive symptoms. A score of 21 or greater indicates severe depressive symptoms. This variable will be treated as a covariate.
Montreal Cognitive Assessment (MoCA)	T1	The MoCA is a brief screener for dementia symptoms. Sixteen items are used to assess short-term memory, language, orientation, and visuospatial abilities. Within the present study, a previously established cut-off score of <23 will be indicative of cognitive impairment.

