 - self-identified activity performance goals per the Canadian Occupational Performance Measure (COPM)
 - upper extremity hemiparesis as indicated by a score of 1-3 on the NIHSS motor arm score

Exclusion Criteria:

- inability to provide informed consent
- severe depressive symptoms as indicated by a score >21 on the Patient Health Questionnaire (PHQ-9)
 - dementia symptoms as indicated by a score of <23 on the Montreal Cognitive Assessment (MoCA)
 - additional neurological diagnoses identified by medical chart review (e.g., brain malignancy)
 - moderate or severe aphasia as indicated by a National Institutes of Health Stroke Scale (NIHSS) aphasia score of 2 or higher
 - no voluntary movement in affected upper extremity as indicated by a score of 4 on the NIHSS motor arm score
 - anosognosia as indicated by an inability to identify activity performance problems on the COPM or PQRS
 - any other condition not otherwise specified that the PI determines would render participation in this study as unsafe
 - currently receiving outpatient rehabilitation for their upper extremity

6. Drugs/ Substances/ Devices

N/A

7. Study Analysis Plan

- a. Primary outcome variable.
- b. Secondary outcome variables.
- c. Statistical plan including sample size justification and interim data analysis.
- d. Early stopping rules.

a. The primary outcome variables will be the COPM, PQRS, and Upper Extremity Fugl-Meyer.
b. The secondary outcome variables will be the NIH Toolbox, PHQ-9, MoCA, SIS, and Life Space Questionnaire.

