c. All data will be cleaned and checked for accuracy. Data accuracy will be evaluated using a double-data entry procedure (see *Data Safety and Monitoring Plan*). As a randomized design we expect the treatment groups to be well balanced. There is always the potential for differential attrition to result in treatment groups that are somewhat imbalanced with respect to potential covariates predictive of the outcomes (see Table 3). Prior to the initial analysis we will examine differences in potential covariates and those that exhibit statistically significant and clinically meaningful differences between groups will be included as covariates in the analysis. The primary analysis for Aims 1 & 2 will be a two-factor (Group, Time) analysis of variance (or covariance) with time the repeated factor. Following a statistically significant time by group interaction effect, contrasts will be constructed to test for group differences by time point and estimate within-group change from baseline at each time point. Estimation will be via maximum likelihood methods that do not require complete data for each participant but do assume the drop out mechanism is non-informative. The primary analysis follows the intention-to-treat principal, but should the groups differ with respect to drop-out or compliance we will treat "dose" as a covariate for a secondary analysis of each aim.

d. This study will be stopped prior to its completion if: (1) the intervention is associated with adverse effects that call into question the safety of the intervention; (2) difficulty in study recruitment or retention will significantly impact the ability to evaluate the study endpoints; (3) any new information becomes available during the trial that necessitates stopping the trial; or (4) other situations occur that might warrant stopping the trial.

8. Risks

There are no expected risks from participation in this study. This expectation is based on the nature of the behavioral study but also on substantial preliminary data across three clinical trials the PI has conducted investigating this specific intervention and/or similar behavioral interventions. The risks associated with participation in this study are no greater than what the subjects may encounter in everyday life. The following risks are considered rare possible risks from participation in this study.

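### The plan never commits to adjusting the between-arm comparison for each primary outcome's own T1 score, and it leaves the contrasts at T2 and T3 undefined on baseline adjustment

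*Combined protocol and SAP*

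**What the plan says.** Section 7c gives the model: "The primary analysis for Aims 1 & 2 will be a two-factor (Group, Time) analysis of variance (or covariance) with time the repeated factor". Potential covariates are to be examined before the first analysis, and "those that exhibit statistically significant and clinically meaningful differences between groups will be included as covariates in the analysis". The between-arm tests come second: "Following a statistically significant time by group interaction effect, contrasts will be constructed to test for group differences by time point". Change from baseline is mentioned in the same sentence, but only for estimates within each group.

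Section 1 (Abstract) names an analysis of covariance within an intent-to-treat analysis. It adds "Potential covariates will include age, stroke severity, degree of cognitive impairment, and degree of motor impairment" and "Group differences at baseline that are statistically significant will also be considered as covariates in the analysis". It also promises that "Significance levels, effect sizes, and confidence intervals will be reported".

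The assessment table in Section 4 lists PHQ-9 at T1, T2 and T3 and states "This variable will be treated as a covariate", without naming a visit. Section 7b then lists the same scale as an outcome: "The secondary outcome variables will be the NIH Toolbox, PHQ-9, MoCA, SIS, and Life Space Questionnaire".

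The three primary outcomes in Section 7a are COPM, PQRS and Upper Extremity Fugl-Meyer. The Section 4 table has all three measured at T1, and Section 4a places T1 before randomization.

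**The concern.** The T1 score of an outcome is usually among its strongest predictors. Here it is collected on everyone before allocation, so adjusting for it is free. The plan instead lets covariates in through a test of observed imbalance, which says little about how well a variable predicts the outcome. It does not say that the own T1 score is always used.

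What is at stake is the between-arm difference at T2 and T3 and its confidence interval. The contrast could be read in three ways: a cross-sectional difference at the visit, a difference in change from T1, or a T1-adjusted difference. In an unconstrained three-visit model with complete data, the group difference at T2 is just the difference between the two T2 means, and T1 does not enter it. On that reading the interval is wider than it needs to be and the estimate carries any chance gap at T1. The gate and the contrast also ask different questions, since one concerns change and the other concerns level. The gate can therefore be passed with no visit at which a difference is found.

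**Working it through.** **1. The texts side by side.**
- Section 7c: a covariate enters if the arms differ both significantly and meaningfully. No threshold is given for the second condition.
- Section 1: four potential covariates, plus significant baseline differences that will be considered.
- Section 4 table: PHQ-9 enters without condition, visit not stated.
- Own T1 score of COPM or PQRS: not named as a covariate in any of the three. For Fugl-Meyer, the abstract's motor impairment item might mean its T1 score, but no instrument is named and the item is only potential.

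**2. Inputs.** The plan has no figure of its own on this point. From the documents: 108 participants (Section 1); pilot effects d = 1.6 and 1.1 for objective trained and untrained activities (Section 3). Assumed: equal allocation (54 per arm), two-sided 0.05, complete data, unit SD, the same correlation ρ between all visits, the same effect d at T2 and T3. Results are given for ρ = 0.3/0.5/0.7/0.8.

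**3. Interval half-width at one visit.** The variance of the difference is (2/54) × f.
- Cross-sectional, f = 1: 1.983 × √(2/54) = 0.38 SD at every ρ.
- Difference in change, f = 2(1 − ρ) = 1.40/1.00/0.60/0.40.
- T1-adjusted, f = (1 − ρ²)(1 + 1/104), the last factor being the small cost of estimating the slope. At ρ = 0.5: 1.983 × √(0.03704 × 0.75 × 1.0096) = 0.33 SD.

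**4. Carry-over of a chance T1 gap.** The expected shift in a cross-sectional contrast is ρ × gap. A gap of 0.20 SD shifts it by 0.5 × 0.20 = 0.10 SD at ρ = 0.5 and by 0.8 × 0.20 = 0.16 SD at ρ = 0.8.

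**5. With the present gate kept, d = 0.5.** The gate is the 2-df group-by-time test, that is, Hotelling's T² on (T2 − T1, T3 − T1). Results come from 40,000 simulated trials per scenario and hold to within about a point.

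| ρ | 0.3 | 0.5 | 0.7 | 0.8 |
|---|---|---|---|---|
| Half-width, cross-sectional (SD) | 0.38 | 0.38 | 0.38 | 0.38 |
| Half-width, change (SD) | 0.45 | 0.38 | 0.30 | 0.24 |
| Half-width, T1-adjusted (SD) | 0.37 | 0.33 | 0.27 | 0.23 |
| Gate passed | 60% | 76% | 94% | 99% |
| Gate passed, neither visit significant: cross-sectional | 3% | 7% | 15% | 18% |
| Same, T1-adjusted | ≤0.5% | ≤0.5% | ≤0.5% | ≤0.5% |
| Gate passed and a difference at T2 or T3: cross-sectional | 58% | 69% | 79% | 81% |
| Same, change | 60% | 76% | 94% | 99% |
| Same, T1-adjusted | 60% | 76% | 94% | 99% |

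**6. What T1 adjustment does to the gate, d = 0.5.**
- T1 as a covariate with only T2 and T3 modelled: the time factor has two levels, so the interaction tests only whether the effect differs between T2 and T3. With equal effects it passes in about 5% of trials at every ρ.
- T1, T2 and T3 modelled with a common T1 mean: the joint 2-df test of the arm differences at T2 and T3 passes in about 87/91/97/99.7%.

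**7. The imbalance screen, only if the own T1 score counts as a Section 7c candidate covariate.** The gap must exceed 1.983 × √(2/54) = 0.38 SD to be significant. A gap above 0.20 SD has probability 0.30, so 0.30 − 0.05 = 0.25 of trials would have a gap of 0.20 to 0.38 SD left unadjusted. An ungated T2 test at d = 0.5 then has power 74/74/75/76%, against 77/84/95/99% when T1 is always used. These figures do not apply if T1 is simply a level of the time factor.

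**The case against.** The strongest defence is that T1 is already in the model. Section 7c takes time as the repeated factor and estimates change from baseline, so the interaction test compares change between the arms. The abstract also says analysis of covariance, which many readers take to mean adjustment for the baseline score. Both points stand in part. A reader might infer that the plan ignores baseline altogether, and the documents do not support that. But the abstract names no T1 score, Section 7c makes covariance optional, and neither defines the contrasts.

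A second defence is that the power loss depends on the reading. If the contrasts are differences in change, gated power equals that of T1-adjusted contrasts. Even on the cross-sectional reading the gated loss is 2 points at ρ = 0.3 and 7 at ρ = 0.5. This stands. It would be tempting to quote the ungated comparison at d = 0.5 (73% cross-sectional against 77/84/95/99%) as the cost to this trial, but Section 7c tests contrasts only after the gate.

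Third, the covariate screen is introduced in the context of differential attrition and refers to a Table 3 that is not in the supplied text. Its absence is not held against the plan. For the same reason the screen figures in step 7 of the working are conditional.

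Fourth, a reader might infer three rival covariate rules. That is too strong: one text is an abstract, and the PHQ-9 sentence concerns a single variable. What remains is wording that does not match and needs reconciling.

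Finally, the pilot effects on objective activities are so large that the loss of power vanishes. That is true at d of 1.1 or more. Section 3 gives no pilot effect for COPM, however, and only r = 0.3 for motor function.

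**Conclusion.** The concern holds in a limited form. The covariate wording in Sections 1, 4 and 7c does not agree. No section fixes the own T1 score of each primary outcome as an adjustment, and the between-arm contrasts at T2 and T3 are not defined as baseline-adjusted. If they are cross-sectional, the cost is avoidable imprecision (slight at ρ = 0.3, about 40% of the half-width at ρ = 0.8, since 0.23/0.38 = 0.61), exposure to chance T1 gaps, and a risk of passing the gate with nothing significant at either visit. The plan is not invalid, because randomization still protects the comparison.

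The figures rest on assumed allocation, correlation, alpha, effect size and complete follow-up, so they show direction and likely size and are not properties of the plan. A reader might also infer that T1 adjustment can be added with the interaction sentence left as it is. For a model of T2 and T3 only, step 6 of the working shows that it cannot. This should be fixed; confidence is medium.

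**What to change.** In Sections 1, 4 and 7c, state one model and one covariate list, both fixed in advance, and drop covariate selection by baseline significance tests. For each primary outcome, always adjust for its own T1 score, and define the T2 and T3 between-arm contrasts as baseline-adjusted differences.

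The simplest form that keeps T1 in the time factor is a likelihood-based repeated-measures model of T1, T2 and T3 with a common T1 mean across arms. Its gate is the joint 2-df test of the arm differences at T2 and T3. If T1 is instead a covariate in a model of T2 and T3, reword the gate as the joint test of the arm effects at both visits, or replace it with one time point named in advance. Which of these to use is for the sponsor to decide. With a joint 5% gate, the chance of any false claim under no effect cannot exceed 5% per outcome. Ungated T1-adjusted tests at both visits would give about 9–10%.

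If PHQ-9 stays a covariate, specify its T1 value, because later scores follow randomization and are a listed secondary outcome.

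The cost is wording only, including the gate sentence, with no extra data, visits or patients.

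### Section 7c chooses covariates for the primary model by observed group differences, and the Abstract and the PHQ-9 entry state other rules, so the adjusted model is not fixed in advance

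*Combined protocol and SAP*

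**What the plan says.** Section 7c makes the primary analysis for both aims a "two-factor (Group, Time) analysis of variance (or covariance) with time the repeated factor", fitted by maximum likelihood. Group contrasts at each time point follow only after a significant interaction. As the reason for looking at covariates it gives the "potential for differential attrition to result in treatment groups that are somewhat imbalanced with respect to potential covariates predictive of the outcomes", and it cites Table 3. It then says that "those that exhibit statistically significant and clinically meaningful differences between groups will be included as covariates in the analysis". It defines no threshold for either condition.

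The Abstract commits to an ANCOVA and says: "Potential covariates will include age, stroke severity, degree of cognitive impairment, and degree of motor impairment". It adds: "Independent samples t-test and chi-square test will be used to ensure successful randomization and balance between groups", and then: "Group differences at baseline that are statistically significant will also be considered as covariates in the analysis".

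The assessment table in section 4a schedules PHQ-9 at T1, T2 and T3 and says: "This variable will be treated as a covariate". It names neither the model nor the time point. Section 7b also lists PHQ-9 as a secondary outcome.

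No section ranks these statements or gives a final covariate list.

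**The concern.** For the same data the primary model could carry no covariate (the usual result of the 7c screen), at least PHQ-9 (section 4a), or the Abstract's four plus any that differ (one reading of the Abstract). Which of these is fitted is not settled before the group differences are known.

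The screen also works against its stated purpose. Section 7c starts from candidates said to predict outcome but then selects among them on imbalance, so prognostic variables are usually left out. It cites attrition as the reason, yet does not say whether the comparison covers everyone randomised or only those remaining; the Abstract tests baseline differences to check randomisation. Maximum likelihood assumes non-informative drop-out, which is more plausible when predictors of drop-out are in the model.

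Finally, 7c does not say whether covariates interact with time. With complete data a main-effect covariate leaves the group-by-time test unchanged, so even an admitted covariate might do nothing for the test that gates the rest. At stake are some precision, protection against differential attrition, and a model fixed in advance for all three primary outcomes.

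**Working it through.** The documents give no figure on this point to reproduce. They give N = 108 but no alpha, allocation ratio, dropout rate or correlations. Assumed below: two-sided 0.05, 54 per arm, the Abstract's four candidates, outcomes and covariates in SD units.

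**1. The rules side by side**

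| Place | Entry rule | Fixed in advance? |
|---|---|---|
| 7c | Significant and clinically important group difference | No |
| Abstract | Four potential covariates; significant differences also considered | List yes, entry unclear |
| 4a, PHQ-9 | Unconditional | Yes, but no time point |

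**2. How often nothing enters, without differential attrition**

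Independent candidates: 0.95^4 = 0.8145. With mutual correlation 0.3 or 0.5 (1,000,000 draws): 0.826 or 0.844. The clinical condition can only raise these. A longer Table 3 lowers them: 0.95^5 = 0.77, 0.95^10 = 0.60.

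**3. Precision of the change-from-T1 contrast**

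Let r be the T1-follow-up correlation, and c1 and c2 the covariate's correlations with T1 and follow-up. Change has variance 2(1-r), of which the covariate explains (c2-c1)^2. Without the covariate, 108 participants are worth 108 x [1 - (c2-c1)^2 / (2(1-r))].
- c1 = c2: 108, no loss.
- c1 = 0.3, c2 = 0.5, r = 0.5: 108 x (1 - 0.04/1.0) = 103.7.
- c1 = 0.3, c2 = 0.5, r = 0.8: 108 x (1 - 0.04/0.4) = 97.2.

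From an assumed 80% power, Phi(2.80 x sqrt(N/108) - 1.96) gives about 78% and 76%.

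**4. The screen as a guard against attrition**

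Dropout depends on one covariate, with log-odds 1 per SD in one arm and 0 or -1 in the other. Imbalance D among those remaining comes from numerical integration; the flag rate is two-sample t-test power with 48.6 or 43.2 per arm.

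| Dropout, log-odds | D (SD) | Flagged |
|---|---|---|
| 10%, 1 vs 0 | 0.09 | 7% |
| 20%, 1 vs 0 | 0.17 | 13% |
| 10%, 1 vs -1 | 0.18 | 15% |
| 20%, 1 vs -1 | 0.35 | 39% |

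Simulation (4,000 trials per setting) gave 7-8%, 13-14%, 14-15% and 40%. If the screen compares everyone randomised, it flags 4-5%.

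**5. Bias when the covariate is left out**

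Maximum likelihood keeps dropouts' T1 outcomes, so the bias is (c2 - r x c1) x D. In the extreme setting (D = 0.346) it runs from (0.5 - 0.8 x 0.5) x 0.346 = 0.035 to (0.5 - 0.5 x 0.3) x 0.346 = 0.121. Simulation gave 0.038-0.124 there and 0.010-0.066 in the other three settings, with standard errors of 0.126-0.215. With covariate-by-time terms the bias was at most 0.006.

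**6. Type I error**

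Without differential attrition: with a single follow-up outcome, five independent candidates and a fixed screening rule (20,000 trials per setting), the screened analysis rejected in 4.0-4.6% of null trials.

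In the extreme setting, without the covariate, rejection is Phi(-1.96 + b/SE) + Phi(-1.96 - b/SE), where b is the bias and SE = sqrt(4(1-r)/43.2). At c1 = 0.3, c2 = 0.5:
- r = 0.5: b = 0.121, SE = 0.215, about 9%.
- r = 0.8: b = (0.5 - 0.8 x 0.3) x 0.346 = 0.090, SE = 0.136, about 10%.

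**The case against.** The strongest defence is that this is loose drafting rather than three competing rules. Section 7c does not say that its screen is the only way in. The Abstract's list is of potential covariates and may be just a candidate set, and the PHQ-9 entry names no model. An additive reading, PHQ-9 plus any imbalanced candidate, is available. This stands as a reading, but no section states it. The Abstract's significance-only condition still differs from 7c's two conditions, and under the additive reading entry still depends on the observed differences.

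Second, Table 3 may hold a longer list, so the 81-84% is not a property of the plan. That stands. But 7c cites the table for potential covariates, so the screen would still apply to whatever it lists.

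Third, maximum likelihood and the secondary analysis with dose as a covariate give some protection, and the gating test does not move with a main-effect covariate in complete data. Both are true and keep the cost modest. They do not settle which model is fitted, and the later contrasts at each time point do change with a main-effect covariate.

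A reader might infer that the screen inflates type I error. Working step 6 does not support that for a fixed rule without differential attrition. A reader might also infer that the model will be picked by its p-value; nothing in the documents says so.

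**Conclusion.** The point holds at a modest size and should be corrected before analysis. The text alone shows that covariate entry in 7c depends on the data and that the Abstract and section 4a state different rules.

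The numbers rest on assumed alpha, allocation, correlations and dropout. For the change-from-T1 contrast the precision loss runs from zero to about 10% of the sample (108 worth 97). The screen misses most moderate imbalances. The bias from omitting a covariate stays below one standard error even in the extreme dropout setting, where it is about 0.04-0.12 SD. The statement that type I error is not inflated is therefore limited to a fixed rule without differential attrition. Without differential attrition the unadjusted interaction contrast is unbiased.

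A larger power loss is tempting to claim: with a single follow-up outcome and no T1, simulated power was 83% prespecified against 74% screened when five covariates explained 25% of variance (true difference 0.5 SD). That is not the 7c model, in which T1 is a level of time, so the figure should not be carried over.

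**What to change.** Replace the covariate sentences in the Abstract, section 4a and section 7c with one prespecified set of T1 covariates, entered whatever the observed balance:
- age;
- stroke severity, with a named measure;
- one named T1 cognitive measure;
- T1 Upper Extremity Fugl-Meyer, not entered as a covariate when it is the endpoint.

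State whether PHQ-9 belongs to the set and, if so, use the T1 value only, because later values could be affected by treatment.

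Keep T1 as a level of the time factor, do not also enter the T1 outcome as a covariate, and add covariate-by-time terms. Report baseline balance, and dropout by arm and covariate, descriptively only.

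If the sponsor prefers a model of T2 and T3 adjusted for the T1 outcome, the interaction gate must be replaced by a test of the group effect at T2 and T3. Otherwise the interaction would ask only whether the effect changes between those visits. In simulation (54 per arm, T2-T3 correlation 0.6) an equal effect of 0.6 SD at both visits passed that gate only about 5% of the time.

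The cost is a reconciled text and a few extra coefficients with 108 participants. Age, T1 cognition and T1 Fugl-Meyer are already collected. Stroke severity needs a named measure, since the documents mention only NIHSS item scores.

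### Section 7c specifies a between-arm difference only after a significant 2-df Group x Time interaction, and no section names the visit that carries the efficacy claim

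*Combined protocol and SAP*

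**What the plan says.** Section 7c defines the main model: "The primary analysis for Aims 1 & 2 will be a two-factor (Group, Time) analysis of variance (or covariance) with time the repeated factor". The next step is conditional: "Following a statistically significant time by group interaction effect, contrasts will be constructed to test for group differences by time point". The same sentence puts a second product behind the condition, namely to "estimate within-group change from baseline at each time point". Section 7c does not say what is constructed or reported when the interaction is not significant.

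Section 7a lists three primary outcomes (COPM, PQRS and Upper Extremity Fugl-Meyer) and attaches no time point to any of them. Section 4a schedules all three at T1, T2 and T3.

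The Abstract (Section 1) calls the efficacy analysis an intention-to-treat ANCOVA and adds, without any condition on significance: "Significance levels, effect sizes, and confidence intervals will be reported". It does not say for which contrast, visit or outcome.

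**The concern.** The aims ask how much better MCST is than usual care. The answer is a between-arm difference with a confidence interval for each primary outcome, and it is needed most when the result is null or equivocal. An omnibus interaction test reacts to any difference in shape between the two curves and does not say in which direction or at which visit. If the difference is constructed only when that test is significant, two things follow. Some primary outcomes may be reported with an estimate and others without. And the estimates that do appear have been selected for being large, which biases them upward when power is modest. With no visit named, it is also open whether success means a benefit at the end of treatment or three months later.

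**Working it through.** **Inputs.** From the documents: total N 108 (Abstract), two arms, three visits, and pilot effects of d = 1.6 and 1.1 for activity performance and r = 0.3 for motor function (Section 3, n = 26). Alpha, allocation ratio, SD, within-person correlation and dropout are not stated. Assumed here: two-sided 0.05, 1:1 allocation (54 per arm), SD 1, equal correlation 0.6 between visits, complete data. Sensitivity: correlation 0.5 and 0.7, and 43 per arm (about 20% loss).

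**The plan's own figure.** N = 108 comes with no power statement, so it can only be back-fitted: (1.960 + 0.842) x sqrt(2/54) = 0.54 SD detectable with 80% power. The pilot r = 0.3 converts, by one common formula, to d = 2 x 0.3 / sqrt(1 - 0.09) = 0.63.

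**Degrees of freedom.** (2 - 1) x (3 - 1) = 2, with T1 as a level of Time, as the planned change-from-baseline contrasts imply.

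**How often the gate opens.** For the two change scores under equal correlation r, a sustained effect d gives the 2-df test a noncentrality of n d^2 / (3(1 - r)). With n = 54 and r = 0.6:
- d = 0.3: 54 x 0.09 / 1.2 = 4.05, gate opens in about 41% of trials.
- d = 0.4: 54 x 0.16 / 1.2 = 7.2, about 66%.
- d = 0.63: 54 x 0.397 / 1.2 = 17.9, about 97%.
- d = 1.1: 54 x 1.21 / 1.2 = 54.5, essentially always.

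Under the null it opens about 5% of the time per outcome.

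**Size of the estimate given a passed gate** (simulation, 10,000 to 20,000 trials per scenario, sustained effect). Mean T2 estimate divided by the truth:

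| True effect (SD) | Change from baseline | Baseline-adjusted | Raw T2 difference |
|---|---|---|---|
| 0.3 | about 1.4 | about 1.3 | 1.1 to 1.2 |
| 0.4 | about 1.2 | – | about 1.06 |
| 0.5 | about 1.08 | – | – |
| 0.63 | 1.01 to 1.02 | – | – |
| 1.1 | 1.00 | – | – |

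(A dash marks a figure not given here.) At 0.3 SD the mean change estimate in trials that miss the gate is 0.70 times the truth. The two parts balance: 0.41 x 1.43 + 0.59 x 0.70 = 1.00. The unselected estimate is unbiased, and the bias comes only from conditioning on the gate.

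**Sensitivity, change estimate, sustained effect.** At 0.3 SD with 54 per arm the excess is 57% at correlation 0.5 and 30% at 0.7. With 43 per arm and correlation 0.5 the mean is 0.51, an excess of 70%. At 0.63 SD it is 3% and nil with 54 per arm, and about 8% with 43 per arm and correlation 0.5. The chance of missing the gate with 54 per arm (correlation 0.5, then 0.7) is 67% or 47% at 0.3 SD, 24% or 6% at 0.5 SD, and 7.5% or under 1% at 0.63 SD.

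**Power of the gate against a 1-df T2 contrast** (54 per arm, correlation 0.6). The T2 change contrast has standard error sqrt(4(1 - r)/n) = sqrt(1.6/54) = 0.172. The baseline-adjusted contrast has sqrt(2(1 - r^2)/n) = sqrt(1.28/54) = 0.154.
- Sustained 0.3 SD: gate 41%, change 41%, baseline-adjusted 48%.
- Sustained 0.4 SD: gate 66%, change 63%, baseline-adjusted 72%.
- 0.4 SD at T2 fading to 0.2 SD at T3: gate 53%, change 64%, baseline-adjusted 72%.

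**The case against.** The strongest reply is that Section 7c is silent about a non-significant interaction and forbids nothing, while the Abstract promises effect sizes and confidence intervals without condition. That stands as far as it goes. A reader might infer that outcomes missing the gate will get no effect estimate, and the documents do not say so. But the Abstract names no contrast or visit, so it narrows the gap without closing it.

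A reader might also infer that the reported effects will be exaggerated. That depends on the true effect and the estimator. At the pilot effects the excess is negligible under the base assumptions. Those effects come from 26 participants, however, and no power calculation shows that each primary outcome will clear the gate comfortably.

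Nor is there a general loss of power. At a sustained 0.3 SD about 9% of trials have a significant T2 change contrast that is never constructed, but about 9% pass the gate with that contrast non-significant. A loss appears only against a baseline-adjusted contrast or when the benefit fades.

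Three further readings should not be pressed. Section 7c speaks of testing group differences and estimating within-group change, but a contrast fitted by maximum likelihood yields an estimate in either case. The ANCOVA label in the Abstract does not contradict a repeated-measures model that allows covariates. And the documents support asking for one named time point, not which one it should be.

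**Conclusion.** The point holds in this limited form. Section 7c ties the between-arm contrasts to a significant 2-df interaction and specifies none otherwise, the Abstract does not resolve this, and no time point is named for the efficacy claim. The main harm is selective display of estimates and an undefined claim. Exaggeration is a conditional harm: with 54 per arm, correlation 0.6 and complete data it is about 10-40% at 0.3 SD depending on the estimator (raw lowest, change highest), and for change about 8% at 0.5 SD, 1-2% at 0.63 SD and nil at 1.1 SD or more. A reader might take this for type I error inflation. It is not, because the gate holds about 5% per outcome under the null. Every simulated figure rests on assumed alpha, allocation, correlation and loss, since the documents state none of them. This is an improvement the sponsor should make, not a flaw that invalidates the trial.

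**What to change.** In Section 7c, state that for every primary outcome the baseline-adjusted MCST minus usual-care difference will be reported at T2 and at T3 with a 95% CI, whatever the interaction p-value. Have the sponsor name in advance which of the two time points carries the efficacy claim. Keep the interaction test as supportive, and make the Abstract and Section 7c describe the same analysis.

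The cost is wording only, with no added visits, data or participants. Reporting the estimates regardless has no downside. Naming a single contrast does have one: if the profile over time is not the expected one, the 2-df test can have more power. For example, if T3 were named and a 0.4 SD benefit at T2 were gone by T3, the T3 contrast would reject only at the 5% null rate. Under equal correlation the 2-df noncentrality is the same as for a sustained effect (7.2), so that test would still reject about 66% of the time. Keeping the interaction as a supportive test preserves that information.
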